4. STUDY REGISTRATION

The patient must willingly consent after being informed of the procedures to be followed, the experimental nature of the treatment, and the potential benefits, alternatives, side-effects, risks, and discomforts. Human protection committee (Institutional Review Board/Ethics Committee [IRB/EC]) approval of this protocol and any associated ICFs are required. Eligible patients who wish to participate in the study will be enrolled into the study.

Registration must occur prior to the initiation of protocol therapy. Patient registration and dose level assignment will be performed by Sarah Cannon Development Innovations, LLC (Development Innovations).

For additional information regarding study registration, please refer to the Study Reference Manual.

5. STUDY DESIGN

This study is a Phase I, first-in-human, open-label dose-escalation study of AC699 given as a single agent. Approximately 100 patients are expected to be enrolled in this study.

AC699 will be administered orally (PO). The starting dose will be 100 mg QD on a 28-day per cycle schedule. During the dose-escalation period the Safety Review Committee (SRC) will decide the next dose level and/or schedule or cohort size. Alternative dose levels, intervals, and/or schedules may be explored based on emerging PK, safety and tolerability data. The study will identify a maximum-tolerated dose (MTD) if possible, with safety and tolerability data (see Section 5.1.1); while the totality of data collected on AC699 may be used to suggest a recommended Phase II dose (RP2D). Should an MTD be established in this Study, the RP2D will be no greater than the MTD in this study.

The study schema is presented in Figure 1.

CONFIDENTIAL

[figure not shown]
Sponsor/Development Innovations Study Numbers: AC699-001/BRE 401

Final Protocol: 07 May 2024 Version 4.0

Figure 1 Study Schema

AC699 Monotherapy

Dose Escalation
Safety, Tolerability, and PK

5.1 Treatment Plan

All patients entering this study will receive AC699 orally (PO). The time of day for administration of AC699 should be consistent. The drug should be taken whole with liquid(s) and with food in the morning. The patient should avoid taking other medications at the same time as AC699. When possible, the patient should take other medications in the evening or separated by a minimum of 4 hours following AC699 dosing. If having the patient delay taking other medications 4 hours following AC699 dosing is not feasible please discuss with the Medical Monitor and document.

On scheduled PK collection days (Cycle 1 Day 1, Cycle 1 Day 15, and Day 1 of Cycles 2, 3, 4, and 6) patients will be instructed to wait until they arrive at the study center to take their study drug when told.

If the patient misses a dose of study drug, the patient should take the dose as soon as possible, but not less than 12 hours before the next dose is due.

If vomiting occurs after taking the study treatment, the patient should be instructed not to retake the dose and record the dose recorded as taken in the dosing diary, noting that the patient vomited and marking the time of vomiting. Patients should take the next scheduled dose of AC699. If vomiting persists, the patient should contact the Investigator.

All patients will be required to complete a paper dosing diary, which should be returned to the clinic for review at each visit. The patient should be instructed to record each date and time the dose was taken in the dosing diary. If a dose is missed, the reason must be noted in the diary. A copy of the dosing diary is provided in the study reference materials.

In addition, patients will be required to record all concomitant medications taken during Cycle 1 Days 1 through 15 on a Concomitant Medication Log. A copy of the concomitant medication log is provided in the study reference materials.

CONFIDENTIAL

Sponsor/Development Innovations Study Numbers: AC699-001/BRE 401

Final Protocol: 07 May 2024 Version 4.0

Patients should be advised to return any unused AC699, in addition to returning any empty packaging. Any remaining empty study drug packaging and dosing diaries will be given to the study staff at the end-of-treatment (EOT) visit.

Dose-Escalation Procedure

The actual number of dose cohorts to be explored in this study will depend on determination of the non-tolerable dose based on DLTs in conjunction with the PK and efficacy signal data. Some dose levels during dose-escalation may be provisional. Based on the review of safety and available PK data by the Safety Review Committee (SRC; See Section 5.1.3), increments of dose-escalation may be different from those indicated. The next dose level will only open after the SRC review of the previous cohort dose and corresponding recommendation. However, patients may be screened for the next dose level prior to the SRC meeting.

Information about the non-tolerable dose will be used along with other safety data, as well as the PK profile observed during the conduct of the study to determine the MTD.

Initial 100 mg Dose Administration

The dose-escalation will begin at 100 mg QD.

The 3+3 Dose-Escalation Design

In this study, 4 dose levels of AC699 are initially planned, with a starting dose of 100 mg QD (see Figure 1). Except for the starting dose (100 mg QD), all dose levels are provisional and may be altered through the SRC review of safety and available PK data. The dose-escalation of this study employs the 3+3 dose-escalation design as the basis. Each cohort enrolls 3 to 4 patients initially to insure at least 3 patients are evaluable. Evaluation of a cohort of the first 3 DLT-evaluable patients is required prior to proceeding to the next dose level. Following the 3+3 design, a cohort will be expanded to 6 patients if a DLT is observed, as further illustrated in Table 2. Dose-escalation will be performed with maximum 2-fold increase between any two consecutive dose levels, until the initially planned highest dose of 600 mg is reached. If supported by clinical data and with the approval from the SRC, higher dose levels may be tested. Pending the totality of clinical data, including but not limited to safety and PK, selected dose levels which have been cleared may be backfilled to expand to approximately 20 patients (per dose level) to further support the evaluation of the objectives set, hereabove. Only the additional backfill patients must have historical documentation of an ESR1 mutation from a tissue sample or blood sample. This does not apply to initial dose-escalation cohorts.

Stopping rules

A cumulative incidence of any of the following treatment-related events will trigger a hold on further patient enrollment for all dose cohorts until the SRC determines if it is safe to continue:

- Grade 4 adverse events (AEs) > 25%,
- Serious adverse events (SAEs) > 25%,
- AEs leading to discontinuation from study > 25%,
- Grade 5 AEs > 10%.

The 3+3 dose-escalation procedure is shown in Table 2.

CONFIDENTIAL

Study Drug: AC699 Sponsor/Development Innovations Study Numbers: AC699-001/BRE 401

Table 2 Dose-Escalation (3+3) Design

Number of Patients with a DLT	Action
0 of 3 patients	Escalate to next dose level
1 of 3 patients	Accrue additional evaluable patients at the current dose level (for a total of up to 6 evaluable patients) ^a
1 of 6 patients	Escalate to the next dose level
2 or more patients in a dose level group of up to 6 patients	The MTD has been exceeded

DLT = dose-limiting toxicity, MTD = maximum-tolerated dose

Dose-Limiting Toxicity

Toxicity will be assessed using the NCI CTCAE Version 5.0 unless otherwise specified. Dose-limiting toxicities thought to be related to AC699 during the DLT period (first 28 days) will be defined as any of the following toxicities if considered at least possibly related to study treatment, i.e., not attributable to the disease or disease-related process under investigation, or other non-study related explanation, and that means at least 1 of the hematologic or non-hematologic criteria below:

Dose-limiting toxicities (DLTs) will be defined as follows:

• Any Grade 5 toxicity

Hematological:

- o Grade 4 neutropenia for >7 days; or febrile neutropenia (ANC <1000/mm³ with a single temperature of >38.3° C [101° F] or a sustained temperature of ≥ 38° C [100.4° F] for more than 1 hour)
- o Grade 4 thrombocytopenia; or Grade 3 thrombocytopenia associated with clinically significant bleeding, including any bleeding that warrants a platelet transfusion
- o Grade 4 anemia (life-threatening consequences requiring urgent interventions)

• Non-hematological:

- o Grade 3 or 4 non-hematologic toxicity, with the **exception of**:
 - Alopecia;
 - Grade 3 nausea, vomiting, or diarrhea if well-controlled by supportive care within 72 hours;
 - Grade 3 skin rash that improves in ≤7 days, with or without supportive care;
 - Grade 3 fatigue that improves in ≤ 7 days, with or without supportive care;
 - Grade 3 endocrinopathies that only require treatment with hormone replacement therapy;

CONFIDENTIAL

Sponsor/Development Innovations Study Numbers: AC699-001/BRE 401

Final Protocol: 07 May 2024 Version 4.0

^a For a patient to be considered "evaluable," he or she must have met the minimum safety evaluation requirements of the study, and/or experienced a DLT.

- Grade 3 non-hematologic laboratory abnormalities, other than liver function tests, will not be considered a DLT unless they are associated with clinical manifestations which lead to medical intervention and/or hospitalization
- Potential drug-induced livery injury consistent with Hy's Law (Appendix E),
 defined as AST and/or ALT > 3 × ULN with concurrent total bilirubin > 2 × ULN
 without findings of cholestasis (alkaline phosphatase [ALP] >2 × ULN)
- Grade 3 or higher electrolyte abnormality that lasts > 72 hours, unless the patient
 has clinical symptoms, in which case all Grade 3 or higher electrolyte abnormality
 regardless of duration should count as a DLT

Determination of Dose-Limiting Toxicities

The patient population used for determination of DLTs will consist of patients who have met the minimum safety evaluation requirements of the study, and/or who have experienced a DLT. Minimum safety evaluation requirements will be met if, during Cycle 1 of treatment, the patient receives at least 75% of planned total doses of AC699, completes all required safety evaluations, and is observed for at least 28 days following the first dose of AC699. Patients who have experienced a DLT may be allowed to continue treatment at a lowered dose, if in the opinion of the Investigator, Medical Monitor, and Sponsor, they continue to derive benefit.

Patients who discontinue treatment early due to disease progression or withdrawal will be asked to have all EOT safety evaluations performed as described in the protocol (see Section 7.6). If a patient withdraws from treatment during Cycle 1 due to any reason other than DLT and does not meet the minimum requirements for DLT assessment, that patient will be replaced.

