6.2 Dose Modifications due to Non-Hematologic Toxicity

Dose modifications due to non-hematologic toxicities are shown in Table 4.

Table 4 Dose Modifications due to Grade 3 or 4 Non-Hematologic Toxicities

Toxicity Grade	AC699 Dose ^a	
Grade 3 (except nausea, vomiting, alopecia, diarrhea, rash, and fatigue)	Hold ^a until recovery to ≤ Grade 1 or baseline	
Toxicity resolves in ≤7 days	Resume at original dose	
Toxicity resolves >7 days and <3 weeks	Reduce by 1 dose level	
Toxicity does not resolve to ≤ Grade 1 or baseline within 3 weeks	Discontinue treatment. If in the patient's best interest, dose may be resumed at a lower dose only after discussion and agreement with Medical Monitor.	
Recurrence of the above same toxicity	Hold ^a until recovery to ≤ Grade 1 or baseline	
Toxicity resolves ≤7 days	Resume at original dose or reduce by 1 dose level at the Investigator's discretion ^b	
Toxicity resolves >7 days	Discontinue treatment. If in the patient's best interest, dose may be resumed at 1 reduced dose level only after discussion and agreement with Medical Monitor.	
Grade 4 (except asymptomatic electrolyte abnormalities that respond to treatment and resolve to ≤ Grade 2 within 72 hours, nausea, vomiting, alopecia, diarrhea, rash, and fatigue)	Discontinue treatment	
	Hold ^a	
Grade 4 asymptomatic electrolyte abnormalities that respond to treatment and resolve to ≤ Grade 2 within 72 hours	Once resolved as mentioned, treatment may continue at 1 reduced dose level at the Investigator's discretion and upon discussion with Medical Monitor	
Grade 3 or 4 nausea, vomiting diarrhea, rash and fatigue	Hold and institute maximum supportive treatment until recovery to \leq Grade 1, baseline or tolerable Grade 2	
Toxicity resolves ≤7 days	Resume at original dose	
Toxicity resolves >7 day and <3 weeks	Reduce by one dose level ^b	

CONFIDENTIAL

Study Drug: AC699 Sponsor/Development Innovations Study Numbers: AC699-001/BRE 401

Toxicity Grade	AC699 Dose ^a
Toxicity does not resolve to \leq Grade 1 or baseline, or tolerable Grade 2 by 3 weeks	Discontinue treatment. If in the patient's best interest, dose may be resumed at a lower dose only after discussion and agreement with Medical Monitor.
Recurrence of the above same toxicity	Hold and institute maximum supportive treatment until recovery to \leq Grade 1, baseline or tolerable Grade 2
Toxicity resolves ≤7 days	Resume at original dose or reduce by one dose level at the Investigator's discretion ^b

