10.2 Sample Size Considerations

The actual number of dose levels to be explored in this study will depend on determination of the non-tolerable dose based on DLTs. The MTD will be defined based on DLTs. Other safety data, as well as PK profiles observed during the conduct of the study and any trends for anti-tumor activity will also be collected. Treatment cycles will occur consecutively as per the Schedule of Assessments. If one patient experiences a DLT at a given dose level, then that dose level will be expanded to 6 patients. Evaluation of a cohort of at least 3 patients completing 1 cycle of treatment (28 days) is required prior to proceeding to the next dose level. In addition, selected dose levels may be expanded to approximately 20 patients (per dose level).

The study will enroll approximately 100 patients, but the actual number will depend on the actual data.

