7.1 Pharmacokinetic Analysis

Plasma concentrations of AC699 will be summarized descriptively at each timepoint.

Plasma concentrations of AC699 will be used to calculate the PK parameters. These parameters will be listed by individual patient and summarized by descriptive statistics (means, medians, ranges, standard deviations, and coefficients of variation as appropriate) by cohort.

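### DLT evaluability in Section 5.1 sets no condition on amount received or assigned dose level, so an under-exposed patient can be scored as tolerating that level

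*Protocol*

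**What the plan says.** Section 5.1 (Determination of Dose-Limiting Toxicities) admits to the DLT count patients who had a DLT, and patients without one who met minimum requirements in Cycle 1. Those requirements are that "the patient receives at least 75% of planned total doses of AC699", and that the patient "completes all required safety evaluations, and is observed for at least 28 days following the first dose of AC699". Section 5 fixes the planned number of doses: "The starting dose will be 100 mg QD on a 28-day per cycle schedule", which gives 28.

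Other provisions bear on what those doses may be:

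- **Vomited doses.** Under Section 5.1, "the patient should be instructed not to retake the dose and record the dose recorded as taken in the dosing diary", with the vomiting and its time noted. Section 8.1.2 also says not to retake the dose, but is silent on whether it counts as taken.
- **Grade 3 events that are not DLTs.** The exceptions in Section 5.1 include "Grade 3 fatigue that improves in" 7 days or fewer. Grade 3 rash has a parallel exception.
- **Reductions.** When Grade 3 fatigue or rash recurs and resolves within 7 days, Table 4 in Section 6.2 offers "Resume at original dose or reduce by one dose level", at the investigator's discretion. Section 6 rules out reduction below 100 mg.
- **Escalation.** Table 2 escalates on no DLT in 3 patients or one in 6.
- **Oversight.** Section 5.1.3 has the Safety Review Committee (SRC) consider interruptions and reductions when it decides how to proceed.

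Protocol Section 10.2, repeated in SAP Section 2.3, says "Evaluation of a cohort of at least 3 patients completing 1 cycle of treatment (28 days) is required" before the next level opens. SAP Section 3.3 defines no DLT-evaluable set.

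**The concern.** In a 3+3 design, each DLT-free evaluable patient is taken as evidence that the assigned dose was tolerated for a cycle. The evaluability rule decides whose experience counts as that evidence. If it is met by intakes of any size, a patient who spent half the cycle one level down contributes the same zero to Table 2 as a patient dosed in full. If diary entries are used for the count, a patient who vomited many doses does too.

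The error would not be neutral. If lower exposure means a lower chance of a DLT, such patients make a dose look more tolerable than it is, and the design moves up when it should expand or stop. In a first-in-human trial whose MTD rests on these counts, the rule should not depend on how a reader interprets one phrase.

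**Working it through.** The plan gives no figure for this point and tests no hypothesis, so there is nothing to reproduce. The check is arithmetic on the stated rules.

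**1. The threshold.** 0.75 × 28 = 21 doses, so up to 7 may be missed. A hold of 8 days leaves 20/28 = 71.4%, which is not evaluable. Missed doses alone therefore cannot take an evaluable patient below 75% of the planned amount. Any larger shortfall must come from reductions or vomiting.

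**2. The reduction route (only above 100 mg).** A course the text allows:

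| Days | Dosing | Doses |
|---|---|---|
| 1-4 | assigned level | 4 |
| 5-7 | held, Grade 3 fatigue | 0 |
| 8-11 | assigned level | 4 |
| 12-14 | held, recurrence | 0 |
| 15-28 | one level down | 14 |

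- By count: (4 + 4 + 14)/28 = 22/28 = 78.6%, so evaluable. Each episode improves within 7 days, so neither is a DLT.
- At the assigned level: 8 of 28 doses.
- By milligrams, with the lower level a fraction q of the assigned one: (8 + 14q)/28. Section 5.1 caps steps at 2-fold, so q is at least 0.50, giving 15/28 = 53.6%. With q = 0.67 (an assumed 600 to 400 mg step), 17.33/28 = 61.9%.
- The share reaches 75% only if q = (21 − 8)/14 = 0.93 or more.

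Table 3 gives a second route. Recurrent Grade 4 neutropenia, in short afebrile episodes that are not DLTs, leads to resumption one level down. With 9 full, 6 held and 13 reduced doses, the count is again 22/28 = 78.6%, and the amount is (9 + 13q)/28 = 55.4% to 63.1%.

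**3. The vomiting route.** Assume a vomited dose is wholly lost and that the diary entry decides the count. With 28 doses recorded and 8 vomited, the patient is at 100% by count and 20/28 = 71.4% by amount. Section 6 has patients with toxicity of Grade 2 or lower continue without reduction, so lower-grade vomiting need not interrupt dosing.

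**4. Effect on escalation.** With DLT risk p in every patient, P(escalate) = P(0/3) + P(1/3) × P(0/3 in the next three). The risks below are assumptions.

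- p = 0.40, all fully exposed: 0.216 + 0.432 × 0.216 = 0.309.
- One of the first three at 0.20: P(0/3) = 0.6 × 0.6 × 0.8 = 0.288; P(1/3) = 2 × 0.4 × 0.6 × 0.8 + 0.6 × 0.6 × 0.2 = 0.456; total 0.288 + 0.456 × 0.216 = 0.386.
- The same comparison at p = 0.30, with one patient at 0.15: 0.494 rises to 0.564.

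**The case against.** The best reply is that the rule is incomplete rather than wrong, and that the SRC closes the gap. Several parts of that reply stand.

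- Section 5.1 does not say outright that size is irrelevant. SAP Section 6.1.1.1 takes planned dose as the dose first assigned, which could support reading a reduced dose as not a planned one. But that definition serves relative dose intensity and is not tied to evaluability, so the ambiguity remains.
- A reader might infer that vomited doses certainly count towards the 75%. The documents do not say so. The criterion speaks of doses received, and the diary instruction also flags the vomiting. What is missing is a rule linking the two.
- A reader might infer that such a patient mostly did not receive the dose. In the fatigue example that is true of doses at the assigned level (8 of 28) but not of milligrams (54-62%). By vomiting alone, falling below half would take 15 of 28 recorded doses, or 8 of 21. Grade 3 vomiting not controlled within 72 hours is itself a DLT, and Grade 3 or 4 vomiting calls for a hold.
- The fatigue example needs two Grade 3 episodes within two weeks and a discretionary reduction. It cannot occur at 100 mg.
- The assumed halving of risk has no source in the documents. A patient reduced after two Grade 3 events may be more susceptible than average, not less.
- Section 10.2 might seem to set a competing standard. Its wording is compatible with the 28-day observation in Section 5.1.

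The SRC argument stands only in part. The committee must consider interruptions and reductions and may expand a cohort. But it has no threshold, vomited doses are not named, and the Table 2 count does not change. Section 5.1.3 provides for case-by-case inclusion or exclusion of ineligible patients who meet evaluability; nothing equivalent covers under-exposed ones.

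Finally, because "Plasma concentrations of AC699 will be summarized descriptively at each timepoint" under SAP Section 7.1, a reader might infer that vomited profiles understate the PK used to choose the next dose. The documents do not support this: the SAP's final analysis follows the last visit and database lock, whereas the SRC reviews emerging PK under Section 5.1.3.

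**Conclusion.** The concern holds in a limited form. Evaluability without a DLT is not tied to amount, assigned level or vomiting status. On its most natural reading, a patient above 100 mg can meet it with 78.6% of doses but about 54-62% of planned milligrams, and be counted as tolerating a level taken on 8 of 28 days. Those figures rest on the illustrated course and on a lower level at 0.50-0.67 of the assigned dose.

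The tilt towards escalation is conditional. If one of the first three patients has half the DLT risk, P(escalate) rises by about 0.08 at an assumed risk of 0.40 (0.31 to 0.39) and by 0.07 at 0.30 (0.49 to 0.56). The documents give no basis for how often this would happen, or for its being more common at higher doses. The change is still worth making, because this rule feeds every escalation decision and the data needed are already collected.

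**What to change.** - **Section 5.1.** Define evaluability without a DLT as receipt of at least 75% of the planned cumulative Cycle 1 dose in milligrams, the denominator being the planned number of doses times the assigned dose. Keep the existing conditions on safety evaluations and 28-day observation.
- **Vomited doses.** For this calculation, do not count a dose vomited within an interval after intake that is fixed in advance. Reconcile Sections 5.1 and 8.1.2 on how such doses are recorded.
- **Section 10.2 and SAP Section 2.3.** Refer to this one definition.
- **Shortfall caused by AC699-related toxicity.** Report the patient to the SRC with that toxicity, and do not replace the patient as uninformative. Otherwise the amended rule would itself remove toxicity from the count. State beforehand how such a patient enters the Table 2 decision.
- **Optional, minor.** In SAP Section 7.1, flag Day 1 or Day 15 profiles that follow a vomited dose, list them, and leave them out of the final PK summaries.

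The cost is a few lines of wording. The diary already records vomiting times, and the SAP already computes milligram dose intensity against the assigned dose. The downside is that a cohort will occasionally need one more patient.
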